Attachment 9.	Protocol JVDF Amendment(b) Summary An Open-Label, Multicenter, Phase 1 Study of Ramucirumab plus Pembrolizumab in Patients with Locally Advanced and Unresectable or Metastatic Gastric or Gastroesophageal Junction Adenocarcinoma, Non-Small Cell Lung Cancer, Transitional Cell Carcinoma of the Urothelium, or Biliary Tract Cancer.....	122

1. Synopsis

Title of Study: An Open-Label, Multicenter, Phase 1 Study of Ramucirumab plus Pembrolizumab in Patients with Locally Advanced and Unresectable or Metastatic Gastric or Gastroesophageal Junction Adenocarcinoma; Non-Small Cell Lung Cancer; Transitional Cell Carcinoma of the Urothelium; or Biliary Tract Cancer

Summary of Study Design:

Study I4T-MC-JVDF is an open-label, multicenter Phase 1 study to evaluate the safety and efficacy of ramucirumab in combination with pembrolizumab. Phase 1a (dose-limiting toxicity [DLT]) and Expansion Phase 1b (safety and preliminary efficacy) will include patients with locally advanced and unresectable or metastatic gastric or gastroesophageal junction adenocarcinoma; non-small cell lung cancer (NSCLC); transitional cell carcinoma of the urothelium (urothelial cancer); or biliary tract cancer (BTC). If sufficient tolerability and preliminary efficacy are demonstrated in Phase 1, the protocol will be amended to further evaluate efficacy and safety, and re-submitted accordingly.

Objective(s)/Endpoints

	Objectives	Endpoints
Phase 1a and 1b	Primary: To assess the safety and tolerability of 2 dosing regimens of ramucirumab plus pembrolizumab	Dose-limiting toxicities, observed during a 21-day treatment cycle Safety (include but are not limited to): TEAEs, SAEs, deaths, laboratory abnormalities, vital signs, and physical exams
	Secondary: To characterize the PK of ramucirumab when co-administered with pembrolizumab	PK: C_{min} and approximate C_{max} of ramucirumab in serum
Phase 1b	Secondary: To assess the preliminary efficacy of ramucirumab plus pembrolizumab	Efficacy: 
 • ORR (RECIST 1.1 and irRECIST) • DCR, DOR, TTR, PFS, and OS

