3. Objectives and Endpoints

Objective(s)/Endpoints

	Objectives	Endpoints
Phase 1a and 1b	Primary: To assess the safety and tolerability of 2 dosing regimens of ramucirumab plus pembrolizumab	Dose-limiting toxicities, observed during a 21-day observation period Safety (include but are not limited to): TEAEs, SAEs, deaths, laboratory abnormalities, vital signs, and physical exams)
	Secondary: To characterize the PK of ramucirumab when co-administered with pembrolizumab	PK: C_{min} and approximate C^{max} of ramucirumab in serum
Phase 1b	Secondary: 
 To assess the preliminary efficacy of ramucirumab plus pembrolizumab 	Efficacy: 
 ORR (RECIST 1.1 and irRECIST) DCR, DOR, TTR, PFS, and OS
	Tertiary/Exploratory: 
 To explore the association between biomarkers and clinical outcomes To characterize biomarker measures of immune functioning and angiogenesis To assess immunogenicity of ramucirumab when co-administered with pembrolizumab 	Biomarkers: research on genetic and circulating factors Immunogenicity: anti-ramucirumab antibody

NOTE: For a more complete description of terms and abbreviations, see [Attachment 8](#).

Abbreviations: C_{max} = maximum concentration; C_{min} = minimum concentration; DCR = disease control rate;

DOR= duration of response; irRECIST= immune-related RECIST; ORR = objective response rate; OS = overall survival; PFS = progression-free survival; PK = pharmacokinetics; RECIST = Response Evaluation Criteria In Solid Tumors; SAEs = serious adverse events; TEAEs = treatment-emergent adverse events; TTR = time to response.

[figure not shown]
4. Study Design

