4.2.1. Dose Selection for Ramucirumab

4.2.1.1. Rationale for Selection of Ramucirumab Dose Schedule 1 (8mg/kg every 3 weeks on Day 1 and Day 8 in Patients with Gastric-GEJ Cancer and BTC)

Ramucirumab Dose Schedule 1 (8 mg/kg on Days 1 and 8; 21-day cycle) was based on exposure-response analyses in REGARD (8 mg/kg every 2 weeks [Q2W]) and RAINBOW (8 mg/kg on Days 1 and 15; 28-day cycle).

Efficacy

Exposure-efficacy response analyses performed on data obtained from REGARD and RAINBOW demonstrated that an increase in exposure is associated with improved efficacy in terms of both overall survival (OS) and progression-free survival (PFS). In both studies, patients with greater-than-median ramucirumab exposure demonstrated significantly longer OS and PFS (smaller hazard ratio [HR]) as compared to patients with less-than-median ramucirumab exposure.

These findings were consistent for all 4 exposure measures tested: minimum concentration after first dose administration ($C_{\min,1}$), minimum concentration at steady state ($C_{\min,ss}$), maximum concentration at steady state ($C_{\max,ss}$), and average concentration at steady state ($C_{ave,ss}$).

Safety

[figure not shown]
Weekly doses of ramucirumab ranging from 2 to 16 mg/kg were evaluated in the Phase 1 Study JVBM. A maximum tolerated dose (MTD) for weekly dosing was identified as 13 mg/kg. Every-2-week (6 to 10 mg/kg) and every-3-week (15 to 20 mg/kg) dose regimens were evaluated in another dose-ranging Study JVBN. All dose regimens in Study JVBN were well tolerated and no MTD was identified in this study.

REGARD demonstrated a well-tolerated safety profile in the gastric-GEJ cancer monotherapy setting. Due to the low incidence of hypertension and neutropenia, no safety-exposure relationship was identified for these treatment-emergent adverse events.

In RAINBOW, the overall safety profile was also considered manageable, although increasing ramucirumab exposure was correlated with increased incidence of Grade 3 or greater hypertension, neutropenia, and leukopenia. There were no Grade 4 or 5 hypertension events. Hypertension was managed primarily by the use of standard antihypertensive medication, and the association of neutropenia with ramucirumab exposure did not appear to translate to an increased risk of febrile neutropenia with higher ramucirumab exposure.

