8.3. Pharmacokinetics

Pharmacokinetic samples to determine ramucirumab PK will be collected as specified in [Attachment 2](#).

Blood samples will be drawn for all patients for the assessment of ramucirumab concentrations in serum (also known as bioanalytical samples). Sampling times were selected to coincide with expected C_{max} and C_{min} and with consideration to draw minimum volume of blood from patients and ensuring that the patients do not need to make an extra visit to provide these samples.

Instructions for the collection and handling of bioanalytical blood samples will be provided by the Sponsor. The actual start and end date and time of ramucirumab infusion administration must be recorded on the eCRF. The actual date and time that each bioanalytical blood sample was drawn must be recorded on the laboratory accession page after the sample is drawn.

Ramucirumab concentrations in bioanalytical serum samples will be measured using a validated assay methodology in a laboratory designated by the Sponsor.

Bioanalytical samples collected to measure ramucirumab concentration will be retained for a maximum of 1 year following last patient visit for the study.

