Cycle 1 Day 1 (1-hr observation period between Ram and Pem infusions)	1	0:00 hr Predose sample ^{b,d}	X (collect prior to start of first infusion)	X	X	X
		2:00 hr Postdose sample ^{c,d}	X (collect approx. 1 hr after Ram infusion ends)			
Cycle 1 Day 8 (Ram only)	8	0:00 hr Predose sample ^{b,d}	X (collect prior to start of infusion)		X	X
Cycle 2 Day 1	22	0:00 hr Predose sample ^{b,d}	X (collect prior to start of first infusion)	X	X	X
Cycle 3 Day 1	43	0:00 hr Predose sample ^{b,d}	X (collect prior to start of first infusion)		X	X
Cycle 4 Day 1	64	0:00 hr Predose sample ^{b,d}	X (collect prior to start of first infusion)	X	X	X
Cycle 5 Day 1	85	0:00 hr Predose sample ^{b,d}	X (collect prior to start of first infusion)	X	X	X
Cycle 7 Day 1	127	0:00 hr Predose sample ^{b,d}	X (collect prior to start of first infusion)	X	X	X
Cycle 7 Day 8 (Ram only)	134	0:00 hr Predose sample ^{b,d}	X (collect prior to start of infusion)		X	X
Cycle 9, Day 1	169	0:00 hr Predose ^{b,d} 2:00 hr Postdose ^{c,d}	X (collect prior to start of first infusion) X (collect approx. 1 hr after Ram infusion ends)	X	X	X
30 days Post treatment DC		Anytime ^g	X	X	X	X

Schedule 1 (Gastric GEJ Cohort A [2nd-3rd Line] and Gastric GEJ A2 [1st Line]; and BTC Cohort A1 [2nd-3rd Line]): Pharmacokinetic (PK), Immunogenicity (IK), and Biomarker Collection Timepoints for Ramucirumab for Schedule 1 Dosing Regimen (1h Infusion Ramucirumab followed by 0.5h Infusion Pembrolizumab on Day 1 and 1h Infusion Ramucirumab on Day 8, every 3 weeks) (concluded)

Note: Ram and Pem infusions are given every 3 weeks. 1-hr Ram infusion is given prior to half-hour Pem infusion. There is one-hour observation period (for infusion reactions) between Ram and Pem infusions at Cycle 1 Day 1 visit. Each cycle is a 21-day cycle.

Abbreviations: DC = Discontinuation; eCRF = electronic case report form; GEJ = gastroesophageal junction; IK = immunogenicity; IRR = infusion-related reaction; Pem = pembrolizumab; PMBC = peripheral blood mononuclear cells; PK = pharmacokinetics; Ram = ramucirumab.

- a All sample times are relative to start of first (Ram) infusion.
- b Predose sample for Ram PK, IK, and biomarkers should be preferably collected within 1 hour prior to start of first infusion, and within 15 minutes of one another.
- c Two-hour sample for Ram PK should be preferably collected at 1 hr \pm 15 minutes from the end of Ram infusion.

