5.3.12. Pharmacokinetic/Pharmacodynamic Analyses

The sampling schedule for drawing blood samples for ramucirumab PK is provided in Attachment 2 of the protocol. Serum concentrations of ramucirumab prior to infusion (minimum concentration [C_{min}]) and at 1 hour after the end of the ramucirumab infusion (approximately maximum concentrations) will be summarized using descriptive statistics. Population PK analyses for ramucirumab may be conducted using population PK approach. The relationship between ramucirumab exposure and selected safety outcomes may be explored. All PK/pharmacodynamics analysis and creation of tables, figures, and listings will be the responsibility of the Lilly Global PK/pharmacodynamic and Pharmacometrics group based on applicable Global PK/pharmacodynamic and Pharmacometrics Standard Operating Procedures and software approved by the Global PK/pharmacodynamic and Pharmacometrics group's management.

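### Schedule 1 has no scheduled PK sample after a Day 8 infusion, so its reported Cmax is the lower of two within-cycle peaks, and Day 8 pre-dose values are not separated from Cmin

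*Protocol*

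**What the plan says.** The regimen is given in Protocol 4.2.1.1: "Ramucirumab Dose Schedule 1 (8 mg/kg on Days 1 and 8; 21-day cycle"). The gaps between ramucirumab doses therefore alternate between 7 and 14 days.

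The PK objective is secondary, for Phases 1a and 1b: "To characterize the PK of ramucirumab when co-administered with pembrolizumab". Its endpoint in the Synopsis is "PK: C_{min} and approximate C_{max} of ramucirumab in serum". Protocol 8.3 states the aim of the sampling plan: "Sampling times were selected to coincide with expected C_{max} and C_{min").

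In Table ATT.2.1 (Schedule 1) the post-infusion entry, "X (collect approx. 1 hr after Ram infusion ends"), appears twice, at Cycle 1 Day 1 and Cycle 9 Day 1. The two Day 8 rows, "Cycle 1 Day 8 (Ram only") and "Cycle 7 Day 8 (Ram only"), each carry one pre-dose sample and no post-dose sample. Day 1 pre-dose samples after the start of treatment fall at Cycles 2, 3, 4, 5, 7 and 9.

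SAP 5.3.12 says which values are summarized: "Serum concentrations of ramucirumab prior to infusion (minimum concentration [C_{min}]) and at 1 hour after the end of the ramucirumab infusion", the latter being called approximately maximum. Protocol 9.6 uses the same labels. Neither separates Day 8 from Day 1.

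**The concern.** When a second dose follows the first after 7 days and the next dose only after 14, the higher peak in the cycle follows the Day 8 infusion. The table samples after Day 1 infusions only, so the Schedule 1 Cmax describes the lower peak. That conflicts with the aim stated in Protocol 8.3.

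Three things are at stake.

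- **A named endpoint.** Approximate Cmax is a secondary endpoint, and Schedule 1 covers Cohorts A, A1 and A2, which is 15 + 25 + 25 = 65 of the 155 Phase 1b patients.
- **The DLT window.** DLTs are observed over Cycle 1, and Protocol 9.8 has Phase 1a safety and PK data reviewed before expansion. The highest ramucirumab level in that window follows Day 8 and has no scheduled measurement.
- **Exposure and safety.** Protocol 4.2.1.1 reports that higher exposure in RAINBOW went with more Grade 3 or greater hypertension, neutropenia and leukopenia, and it counts Cmax,ss among its four exposure measures. Protocol 9.6 foresees exposure-safety exploration here.

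A smaller labelling problem sits beside this. Under one label for all pre-infusion values, the Cycle 7 Day 8 sample, drawn 7 days after a dose and mid-cycle, would be reported as a minimum.

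**Working it through.** **Figures in the plan.** No half-life or predicted peak is given, so there is no stated Cmax to reproduce. Two related figures confirm the reading of the regimen. Planned intensity is 2 × 8 / 3 = 5.33 mg/kg/week (SAP 5.2.1.2: 5.3). Relative to the 13 mg/kg weekly maximum tolerated dose, 1 − 5.33/13 = 59% (Protocol 4.2.1.1: about 60%). The claim there that at least 70% of patients exceed the median Cmin,ss of the 2-weekly regimen cannot be checked, because the model and the figure values are not available.

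**Direction, without a half-life.** Assume linear PK, full doses given on time, and any declining single-dose curve f. In Cycle 1 the Day 8 peak exceeds the Day 1 peak by f(7). At steady state the excess is [f(7) − f(14)] + [f(28) − f(35)] + …, in which every bracket is positive. The pre-dose difference, Day 8 minus Day 1, is the same sum.

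**Size, with an assumed half-life.** One compartment, unit bolus doses on Days 1 and 8 every 21 days, k = ln 2 / half-life, x = exp(−7k):

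- Cycle 1 peak ratio, Day 8 / Day 1 = 1 + x
- Steady-state peak ratio, Day 8 / Day 1 = (1 + x) / (1 + x²)
- Steady-state pre-dose ratio, Day 8 / Day 1 = (1 + x²) / (x + x²)
- Cycle 1 Day 8 pre-dose / Day 22 pre-dose = x / (x² + x³) = 1 / (x + x²)

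| Half-life, days (assumed) | Cycle 1 peak ratio | Steady-state peak ratio | Steady-state pre-dose ratio | Cycle 1 Day 8 pre-dose / Day 22 pre-dose |
|---|---|---|---|---|
| 5 | 1.38 | 1.21 | 2.19 | 1.91 |
| 7 | 1.50 | 1.20 | 1.67 | 1.33 |
| 10 | 1.62 | 1.17 | 1.39 | 1.01 |
| 14 | 1.71 | 1.14 | 1.24 | 0.83 |
| 21 | 1.79 | 1.10 | 1.14 | 0.70 |
| 28 | 1.84 | 1.08 | 1.10 | 0.65 |

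Worked row, half-life 7 days: x = 0.5; 1 + 0.5 = 1.50; 1.5 / 1.25 = 1.20; 1.25 / 0.75 = 1.67; 1 / 0.75 = 1.33.

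The last column falls below 1 when x + x² > 1, that is x > 0.618, or a half-life above 7 ln 2 / −ln 0.618 = 10.1 days.

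**Effect of pooling, if it were done.** Averaging the two Day 8 pre-dose values with the six Day 1 troughs, instead of using the six alone, would move the mean by about −4% (28 days) to +26% (5 days).

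**The case against.** The plan promises only an approximate Cmax. Sampling was kept sparse on purpose, to limit blood volume and avoid extra visits (Protocol 8.3). A Day 1 post-dose value is a valid concentration. Population PK could predict the Day 8 peak, and the endpoint is secondary and descriptive. The size of the gap depends wholly on an assumed half-life and a one-compartment model.

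Much of this stands, but it does not remove the point. The word approximate is tied to drawing the sample 1 hour after the end of infusion, not to choosing the lower of two peaks. Population PK may be done but is not committed. The direction needs only linear PK; the size is indeed uncertain.

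Several stronger readings are tempting, and the documents do not support them.

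- *A reader might infer that the Cmin endpoint is wrong or that the Schedule 1 rationale fails.* Section 4.2.1.1 rests on Cmin,ss, and six Day 1 pre-dose samples measure the end-of-cycle trough directly.
- *A reader might infer that every Day 8 pre-dose value is mislabelled.* Section 4.2.1.1 uses Cmin,1, the minimum after the first dose, as an exposure measure. In Schedule 1 that is the Cycle 1 Day 8 pre-dose value. It is also below the Day 22 value when the half-life exceeds about 10.1 days.
- *A reader might infer that the Cmin summary mixes quantities, or that a comparison of schedules is biased.* No text says values are pooled across visits, SAP 5.3.1 lists data by cycle and time point where appropriate, and no formal PK comparison of the schedules is planned.
- *A reader might infer that a Day 8 peak can never be observed.* Samples are drawn if an infusion-related reaction occurs, and one could follow a Day 8 dose. These are unsystematic and do not measure the peak across patients.

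**Conclusion.** The point holds in limited form. No scheduled sample follows a Day 8 infusion, so the Schedule 1 Cmax is a Day 1 value below the cycle peak. Given linear PK and doses on schedule, that is true at any half-life. Over assumed half-lives of 5 to 28 days the Day 8 peak is higher by about 38% to 84% in Cycle 1 and 8% to 21% at steady state. A distribution phase or non-linear PK would change these sizes.

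For Cmin the fault is an undivided label, which takes in the Cycle 7 Day 8 value, about 10% to 119% above the steady-state trough over the same range. Neither the trough data nor the primary safety objective is compromised. The consequence is confined to how peak exposure is described and to any exposure-safety work that uses it.

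**What to change.** **Sampling (Attachment 2, Table ATT.2.1).** Keep the Cycle 9 Day 1 post-infusion sample, which Schedule 2 shares. Add a PK sample 1 hour after the end of infusion at Cycle 1 Day 8 and, if acceptable, at Cycle 7 Day 8. Cycle 1 Day 8 matters more: it lies in the DLT window, whereas Cycle 7 Day 8 is study day 134, which many patients may not reach (Table JVDF.1 gives a median PFS of 2.1 months for ramucirumab alone in gastric cancer).

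**Definitions (Protocol 9.6 and SAP 5.3.12), for Schedule 1.**

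- Cmax: the Day 8 post-infusion value where sampled, with Day 1 post-infusion values labelled as such.
- Cmin: Day 1 pre-dose, from Cycle 2 onward.
- Cmin,1: Cycle 1 Day 8 pre-dose.
- Cycle 7 Day 8 pre-dose: tabulated separately as a mid-cycle value.

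**If no sample is added.** State that the Schedule 1 Cmax is a Day 1 value below the cycle peak, and commit to predicting the Day 8 peak by population PK.

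**Cost.** One or two extra blood draws at existing visits, plus wording changes. At Cycle 1 Day 8 no extra waiting is needed, because Protocol 6.9.1.1.1 already requires vital signs at the end of a 1-hour observation after each of the first two ramucirumab infusions, and this is the second. Cycle 7 Day 8 would add about an hour.

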Attachment 3. Protocol JVDF Clinical Laboratory Tests

Hematology-Local only	Clinical Chemistry-Local and Central^a
Hemoglobin	Serum Concentrations of:
Hematocrit	Sodium
Erythrocyte count (RBC)	Magnesium
Leukocytes (WBC)	Potassium
Absolute Neutrophil Count	Total bilirubin
Lymphocytes	Direct bilirubin (if total bilirubin is above ULN)
Monocytes	Alkaline phosphatase
Eosinophils	Alanine aminotransferase (ALT)
Basophils	Aspartate aminotransferase (AST)
Platelets	Blood urea nitrogen (BUN)
	Creatinine
	Uric acid
	Calcium
	Glucose, random
	Albumin
	Cholesterol
	Creatine kinase (CK)
	Chloride
	Total protein
	Phosphorus
	Lactate dehydrogenase (LDH)
	Pregnancy Test Urine or Serum^c-Local Only
	β-human chorionic gonadotropin (β-hCG)
Coagulation Test^d Local Only	
Prothrombin time (PT) /INR	
Partial thromboplastin time (PTT) or activated PTT (aPTT)	

Abbreviations: INR= International Normalized Ratio; RBC = red blood cells; ULN = upper limit of normal;

WBC = white blood cells.

- a. Local chemistry laboratory testing will be used to determine patient eligibility and decisions for treatment. Central chemistry laboratory testing will be used for subsequent scheduled analyses.
- b. A microscopic exam is required for abnormal results. If urinalysis indicates proteinuria $\geq 2+$ at baseline or during the treatment period, a 24 hour urine collection (to assess protein) must be obtained.
- c. Minimum sensitivity 25 IU/L or equivalent units of β-human chorionic gonadotropin (β-HCG), for women of childbearing potential (WOCBP). If urine pregnancy results cannot be confirmed as negative, a serum pregnancy test will be required.
- d. For both prothrombin time and partial thromboplastin time, the laboratory for each is selected at baseline, and should be followed during the study period.

Attachment 4. Protocol JVDF ECOG Performance Status

ECOG Performance Status

Activity Status	Description
0	Fully active, able to carry on all pre-disease performance without restriction
1	Restricted in physically strenuous activity but ambulatory and able to carry out work of a light or sedentary nature, e.g., light house work, office work
2	Ambulatory and capable of all selfcare but unable to carry out any work activities. Up and about more than 50% of waking hours
3	Capable of only limited selfcare, confined to bed or chair more than 50% of waking hours
4	Completely disabled. Cannot carry on any selfcare. Totally confined to bed or chair
5	Dead.

Source: Oken et al. 1982.

Attachment 5. Protocol JVDF Creatinine Clearance Formula

Note: This formula is to be used for calculating creatinine clearance (CrCl) from **local laboratory results only**.

For serum creatinine concentration in mg/dL:

$$\text{CrCl} = \frac{(140 - \text{age}^a) \times (\text{wt}) \times 0.85 \text{ (if female), or } \times 1.0 \text{ (if male)}}{72 \times \text{serum creatinine (mg/dL)}}$$

For serum creatinine concentration in $\mu\text{mol/L}$:

$$\text{CrCl} = \frac{(140 - \text{age}^a) \times (\text{wt}) \times 0.85 \text{ (if female), or } \times 1.0 \text{ (if male)}}{0.81 \times \text{serum creatinine } (\mu\text{mol/L})}$$

a age in years, weight (wt) in kilograms.

Reference: Cockcroft and Gault 1976.

Attachment 6. Protocol JVDF RECIST Criteria 1.1

Response and progression will be evaluated in this study using the international criteria proposed by the New Response Evaluation Criteria in Solid Tumors (RECIST): Revised RECIST Guideline (version 1.1; Eisenhauer et al. 2009).

Measurability of Tumor at Baseline

Tumor lesions/lymph nodes will be categorized at baseline as measurable or nonmeasurable. Measurable disease is defined by the presence of at least 1 measurable lesion.

Measurable

Tumor lesions: Measured in at least 1 dimension (longest diameter in the plane of measurement is to be recorded) with a minimum size of:

- 10 mm by computed tomography (CT) or magnetic resonance imaging (MRI) scan (slice thickness ≤ 5 mm)
- 10 mm caliper measurement by clinical exam (non-measurable lesions if cannot be accurately measured with calipers)
- 20 mm by chest X-ray.

Malignant lymph nodes: To be considered pathologically enlarged and measurable, a lymph node must be ≥ 15 mm in short axis when assessed by CT scan (CT scan thickness recommended to be ≤ 5 mm).

Nonmeasurable

All other lesions, including small lesions (longest diameter < 10 mm or pathological lymph nodes with ≥ 10 to < 15 mm short axis) as well as truly nonmeasurable lesions. Lesions considered truly non-measurable include: leptomeningeal disease, ascites, pleural/pericardial effusions, lymphangitis cutis/pulmonis, inflammatory breast disease, lymphangitis involvement of skin or lung, abdominal masses/abdominal organomegaly identified by physical exam that is not measurable by reproducible imaging techniques.

Special Considerations for Lesion Measurability

Bone Lesions:

- Bone scan, PET scan or plain films are not considered adequate imaging techniques to measure bone lesions.
- Lytic bone lesions or mixed lytic-blastic lesions, with identifiable soft tissue components, that can be evaluated by cross sectional imaging techniques such as CT or MRI, can be considered measurable lesions if the soft tissue component meets the definition of measurability.
- Blastic bone lesions are non-measurable.

Cystic Lesions:

- Simple cysts should not be considered as malignant lesions (neither measurable nor nonmeasurable)
- Cystic lesions thought to represent cystic metastases can be considered as measurable lesions, if they meet the definition of measurability. If noncystic lesions are presented in the same patients, these are preferred for selection as target lesions.

Lesions with Prior Local Treatment:

- Tumor lesions situated at a previously irradiated area, or in an area subjected to other loco-regional therapy, are non-measurable unless there has been demonstrated progression in the lesion.

Baseline Documentation of Target and Non-Target Lesion***Target Lesions***

When more than 1 measurable lesion is present at baseline, all lesions up to a maximum of 5 lesions total (and a maximum of 2 lesions per organ) representative of all involved organs should be identified as target lesions and will be recorded and measured at baseline. For Study JVDF (Section 8.1.1.3), total of 10 lesions (and a maximum of 5 lesions per organ) could be collected if clinically relevant. Non-nodal Target lesions should be selected on the basis of their size (lesions with the longest diameter), be representative of all involved organs, and can be reproduced in repeated measurements. Measurable lymph nodes are target lesions if they meet the criteria of a short axis of ≥ 15 mm by CT scan. All measurements are to be recorded in the case record form (CRF) in millimeters (or decimal fractions of centimeters [cm]).

Nontarget Lesions

All other lesions (or sites of disease) are identified as nontarget lesions (chosen based on their representativeness of involved organs and the ability to be reproduced in repeated measurements) and should be recorded at baseline. Measurement of these lesions are not required but should be followed as ‘present,’ ‘absent,’ or in rare cases ‘unequivocal progression.’ In addition, it is possible to record multiple nontarget lesions involving the same organ as a single item on the CRF (for example, multiple liver metastases recorded as 1 liver lesion).

Lymph nodes with short axis ≥ 10 mm but < 15 mm should be considered nontarget lesions. Nodes that have a short axis < 10 mm are considered nonpathological and are not recorded or followed.

Specifications by Methods of Measurement

All measurements should be recorded in metric notation, using a ruler or calipers if clinically assessed. All baseline evaluations should be performed as closely as possible to the beginning of treatment and never more than 4 weeks before the beginning of the treatment.

The same method of assessment and the same technique should be used to characterize each identified and reported lesion at baseline and during follow-up. Imaging-based evaluation is

should always be done rather than clinical examination unless the lesion(s) being followed cannot be imaged but are assessed by clinical exam.

An adequate volume of a suitable contrast agent should be given so that the metastases are demonstrated to best effect and a consistent method is used on subsequent examinations for any given patient. If prior to enrollment it is known a patient is not able to undergo CT scans with IV contrast due to allergy or renal insufficiency, the decision as to whether a non-contrast CT or MRI (with or without IV contrast) should be used to evaluate the patient at baseline and follow-up should be guided by the tumor type under investigation and the anatomic location of the disease.

Clinical Lesions: Clinical lesions will only be considered measurable when they are superficial and ≥ 10 mm diameter as assessed using calipers (for example, skin nodules). For the case of skin lesions, documentation by color photography, including a ruler to estimate the size of the lesion is recommended. When lesions can be evaluated by both clinical exam and imaging, imaging evaluation should be undertaken since it is more objective and may be reviewed at the end of the study.

Chest X-ray: Chest CT is preferred over chest X-ray when progression is an important endpoint. Lesions on chest X-ray may be considered measurable if they are clearly defined and surrounded by aerated lung.

CT and MRI: CT scan is the best currently available and reproducible method to measure lesions selected for response assessment. Measurability of lesions on CT scan is based on the assumption that CT slice thickness is ≤ 5 mm. When CT scan have slice thickness >5 mm, the minimum size for a measurable lesion should be twice the slice thickness. MRI is also acceptable in certain situations (for example, for body scans). If there is concern about radiation exposure at CT, MRI may be used instead of CT in selected instances.

Ultrasound: Ultrasound should not be used to measure lesion size. Ultrasound examinations cannot be reproduced in their entirety for independent review at a later date and, because they are operator dependent, it cannot be guaranteed that the same technique and measurements will be taken from one assessment to the next. If new lesions are identified by ultrasound in the course of the study, confirmation by CT or MRI is advised.

Endoscopy, Laparoscopy: The utilization of these techniques for objective tumor evaluation is not advised. However, such techniques can be useful to confirm complete pathological response when biopsies are obtained or to determine relapse in trials where recurrence following complete response or surgical resection is an endpoint.

Tumor Markers: Tumor markers alone cannot be used to assess tumor response. If markers are initially above the upper normal limit, they must normalize for a patient to be considered in complete response (CR). Specific guidelines for both prostate-specific antigen (PSA) response (in recurrent prostate cancer) and CA-125 response (in recurrent ovarian cancer) have been published.

Cytology, Histology: These techniques can be used to differentiate between partial responses (PR) and complete response (CR) in rare cases if required by protocol (for example, residual lesions in tumor types such as germ cell tumors, where known residual benign tumors can remain). When effusions are known to be a potential adverse effect of treatment (for example, with certain taxane compounds or angiogenesis inhibitors), the cytological confirmation of the neoplastic origin of any effusion that appears or worsens during treatment can be considered if the measurable tumor has met criteria for response or stable disease (SD) in order to differentiate between response (or SD) and progressive disease (PD).

Pet Scan (FDG-PET, PET CT): PET is not recommended for lesion assessment. If a new lesion is found by PET, another assessment must be done by CT, unless the PET CT is of diagnostic quality. If CT is done to confirm the results of the earlier PET scan, the date of progression must be reported as the earlier date of the PET scan.

Bone Scan: If lesions measured by bone scan are reported at baseline, it is necessary to repeat the bone scan when trying to identify a complete response (CR) or partial response (PR) in target disease or when progression in bone is suspected.

Response Criteria

Evaluation of Target Lesions

Complete Response (CR): Disappearance of all target lesions. Any pathological lymph nodes (whether target or non-target) must have reduction in short axis to <10 mm. Tumor marker results must have normalized.

Partial Response (PR): At least a 30% decrease in the sum of diameter of target lesions, taking as reference the baseline sum diameters.

Progressive Disease (PD): At least a 20% increase in the sum of the diameters of target lesions, taking as reference the smallest sum on study (including the baseline sum if that is the smallest). In addition to the relative increase of 20%, the sum must also demonstrate an absolute increase of at least 5 mm. The appearance of 1 or more new lesions is also considered progression.

For equivocal findings of progression (for example, very small and uncertain new lesions; cystic changes or necrosis in existing lesions), treatment may continue until the next scheduled assessment. If at the next scheduled assessment, progression is confirmed, the date of progression should be the earlier date when progression was suspected.

Stable Disease (SD): Neither sufficient shrinkage to qualify for PR nor sufficient increase to qualify for PD, taking as reference the smallest sum diameters while on study.

Not Evaluable: When an incomplete radiologic assessment of target lesions is performed or there is a change in the method of measurement from baseline that impacts the ability to make a reliable evaluation of response.

Evaluation of Nontarget Lesions

Complete Response: Disappearance of all nontarget lesions and normalization of tumor marker level. All lymph nodes must be non-pathological or normal in size (<10mm short axis).

Non-CR/ non-PD: Persistence of 1 or more nontarget lesions and/or maintenance of tumor marker level above the normal limits.

Progressive Disease: Unequivocal progression of existing nontarget lesions. The appearance of 1 or more new lesions is also considered progression.

Not Evaluable: When a change in method of measurement from baseline occurs and impacts the ability to make a reliable evaluation of response.

Evaluation of Best Overall Response

The best overall response is the best response recorded from the start of the study treatment until the earliest of objective progression or start of new anticancer therapy, taking into account any requirement for confirmation. The patient's best overall response assignment will depend on the findings of both target and nontarget disease and will also take into consideration the appearance of new lesions. The Best Overall Response will be calculated via an algorithm using the assessment responses provided by the investigator over the course of the trial.

Time Point Response

It is assumed that at each protocol-specified time point, a response assessment occurs. (When no imaging/measurement is done at all at a particular time point, the patient is not evaluable (NE) at that time point.) Table 1 provides a summary of the overall response status calculation at each time point for patients who have *measurable disease* at baseline.

Table 1. Time Point Response: Patients with Target (\pm Non-target) Disease

Target Lesions	Non-Target Lesions	New Lesions	Overall Response
CR	CR	No	CR
CR	Non-CR/non-PD	No	PR
CR	Not evaluated	No	PR
PR	Non-PD or not all evaluated	No	PR
SD	Non-PD or not all evaluated	No	SD
Not all evaluated	Non-PD	No	NE
PD	Any	Yes or No	PD
Any	PD	Yes or No	PD
Any	Any	Yes	PD

Abbreviations: CR = complete response; PR = partial response; SD = stable disease; PD = progressive disease; NE = inevaluable.

Table 2 is to be used when patients have *nonmeasurable* disease only.

Table 2. Time Point Response: Patients with Nontarget Disease Only

Nontarget Lesions	New Lesions	Overall Response
CR	No	CR
Non-CR/non-PD	No	Non-CR/non-PD ^a
Not all evaluated	No	NE
Unequivocal PD	Yes or No	PD
Any	Yes	PD

Abbreviations: CR = complete response; PD = progressive disease; NE = inevaluable; SD = stable disease.

^a non-CR/non-PD is preferred over SD for nontarget disease.

Frequency of Tumor Re-Evaluation

A baseline tumor evaluation must be performed within 4 weeks before patient begins study treatment. Frequency of tumor re-evaluation while on and adapted to treatment should be protocol-specific and adapted to the type and schedule of treatment. In the context of Phase 2 studies where the beneficial effect therapy is not known, follow-up every 6-8 weeks is reasonable. Normally, all target and non-target sites are evaluated at each assessment using the same method. However, bone scans may need to be repeated only when CR is identified in target disease or when progression in bone is suspected.

Confirmatory Measurement/Duration of Response

Confirmation:

The main goal of confirmation of objective response in clinical trials is to avoid overestimating the response rate observed. The confirmation of response is particularly important in *nonrandomized trials* where response (CR/PR) is the primary end point. In this setting, to be assigned a status of PR/CR, changes in tumor measurements must be confirmed by repeat assessments that should be performed no less than 4 weeks after the criteria for response are first met. To confirm a response of CR, a full assessment of all target and nontarget lesions that were present at baseline must occur, including those measured by bone scan. To confirm a PR or SD, a full assessment of target lesions that were present at baseline must occur; assessment of nontargets is not required.

However, in *randomized trial* (Phase 2 or 3) or studies where SD or progression is the primary endpoints, confirmation of response is not required. But, elimination of the requirement may increase the importance of central review to protect against bias, in particular of studies which are not blinded.

In the case of SD, follow-up measurements must have met the SD criteria at least once after start of treatment at a minimum interval not less than 6 weeks measured from **[first dose]**.

Duration of Overall Response

The duration of overall response is measured from the time measurement criteria are first met for CR or PR (whichever is first recorded) until the first date that disease is recurrent or objective progression is observed (taking as reference for PD the smallest measurements recorded on study).

The duration of overall CR is measured from the time measurement criteria are first met for CR until the first date that recurrent disease is objectively documented.

Duration of Stable Disease

Stable disease is measured from the start of the treatment (in randomized trials, from date of randomization) until the criteria for objective progression are met, taking as reference the smallest sum on study (if the baseline sum is the smallest, that is the reference for calculation of PD).

Independent Review of Response and Progression

When objective response (CR + PR) is the primary end point, and when key drug development decisions are based on the observation of a minimum number of responders, it is recommended that all claimed responses be reviewed by an expert(s) independent of the study. If the study is a randomized trial, ideally reviewers should be blinded to treatment assignment.

